Date: 10/18/2020 NCT04129216

*THE EFFECTS OF SHORT-TERM
PREOPERATIVE TREATMENT WITH
HORMONAL THERAPY ON GENE PROFILES
IN
BREAST CANCER*

JHM IRB - eForm A – Protocol

- Use the section headings to write the JHM IRB eForm A, inserting the appropriate material in each. If a section is not applicable, leave heading in and insert N/A.
- When submitting JHM IRB eForm A (new or revised), enter the date submitted to the field at the top of JHM IRB eForm A.

1. Abstract

- Provide no more than a one page research abstract briefly stating the problem, the research hypothesis, and the importance of the research.

Breast cancer is among the most common malignancies in women in the United States. Over the years breast cancer management have dramatically developed from the extensive surgical approach toward the breast conservative approach. This was mainly due to the introduction of chemotherapy and hormonal therapy. Hormonal therapy in particular has been shown to improve the oncological outcomes of the breast cancer. However, while this is well documented in the clinical outcomes. Little is known in regards what happens on the genetic level. As such in this study we would like to study the genetic, molecular and functional outcomes that results after a short term neoadjuvant hormonal therapy on patients with breast cancer.

The hypothesize of this study is that short-term, preoperative hormonal treatment will induce genetic changes associated with reduced proliferation, including lower Ki67 expression, and changes in ER and PR expression as well as reduced ER pathway activity. The data from such investigation will be very helpful in advancing the individualized care to women with breast cancer.

Hypothesis

- We hypothesize that short-term, preoperative hormonal treatment will induce genetic changes associated with reduced proliferation, including lower Ki67 expression, and changes in ER and PR expression. as well as changes in ER pathway activity measures

2. Objectives

The purpose of this study is to evaluate the effects of short-term preoperative treatment with hormonal therapy (tamoxifen, letrozole, and exemestane, administered according to standard of care) on gene expression profiles in patients with breast cancer. As such:

- A. Primary objective is to determine whether there is a reduction in the expression of proliferation marker Ki67, measured by IHC as well as single-gene read out, following short-term preoperative treatment with hormonal therapy.

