Breast cancer is the most common malignancy and the second leading cause of cancer deaths among women [1]. As a heterogeneous and phenotypically diverse disease, breast cancer may necessitate divergent treatment strategies, among which cytotoxic chemotherapy remains an integral part of therapy at any given stage. However, cytotoxic therapy is not considered a “targeted therapy”, because it does not act on cellular pathways involved in cell growth and progression [1]. The real targeted therapy would be based on the identification of a molecular growth pathway and on the modification of its activity in order to block the growth and progression of cancer. With regard to breast cancer, the endocrine manipulation is considered as a targeted therapy [2]. The role of estrogen on tumor cell growth is well established in breast cancer. Identification of the estrogen receptors (ER) provided the first target for anti-estrogenic therapeutic agents [1-3]. Tamoxifen, the prototype SERM (Selective Estrogen Receptor Modulator), has been the gold standard treatment for early and advanced disease and its activity on ER is considered the first form of molecular targeted therapy [1, 4]. Aromatase inhibitors (e.g., anastrozole, letrozole, or exemestane) which directly inhibit the production of estrogen, have shown superiority over tamoxifen in adjuvant and metastatic setting [5-8], also they appear to fare better than tamoxifen in the neoadjuvant setting [8], where therapeutic agents are administered before the main treatment (e.g. in the preoperative phase). Following the success of adjuvant endocrine treatments [9-11], more studies have been emerging with the use of endocrine agents in the neoadjuvant setting (PO24 trial [12], IMPACT trial [13] and PROACT trial [14]). The objective of endocrine therapy in the neoadjuvant setting is primarily to produce sufficient response in the tumor to allow mastectomy in inoperable tumors and potentially breast conservation in patients initially proposed to undergo mastectomy [8]. Treatment response to these “targeted therapies” differs vastly across different populations; even patients with the same stages of disease can have markedly different responses and overall outcome [10]. Therefore, an ideal therapy should be tailored based on individual characteristics so that each patient receives a treatment with an appropriate response and the least adverse effects. Genetic breakthroughs in the last few decades have provided us with a unique opportunity to address this challenge. The emergence of genomic techniques (e.g. complementary DNA microarrays) and their ability to simultaneously measure the expression of thousands of genes have led to the identification of biology-based prognostic profiles [15-18], several of which have been validated and are in clinical use. The development of prognostic profiles has been particularly useful in guiding decision-making about adjuvant therapy along with well-established clinical prognostic factors (e.g. patient age, comorbidity, tumor size, grade, and nodal status) [19]. These molecular prognostic profiles can augment but do not replace classic clinical factors. They offer the potential for use in clinical practice for prognostic stratification and treatment selection for patients with breast cancer, particularly if they are hormone receptor-positive. Among the available prognostic profiles, the Amsterdam 70-gene prognostic profile (Mammaprint) was one of the first gene expression array-based marketed for prognostic purposes [20]. The test was developed using a supervised DNA microarray analysis of gene expression arrays on frozen tissue from primary breast tumors. A mathematical model is used to calculate a score that stratifies patients as having a breast cancer with an associated poor-prognosis (High risk: 29% risk of metastasis after 10 years, without adjuvant treatment) or good-prognosis (Low risk: 10% risk of metastasis after 10 years without adjuvant treatment) [21]. Validation of the Mammaprint gene expression profile demonstrated that the profile is a powerful prognostic factor to predict outcome in lymph node-negative and lymph node-positive breast cancer. Recent reports, that the most important of them is MINDACT trial [22, 23], confirm this predictive value for Mammaprint signature. Although it was originally approved for use with unfixed, frozen tissue, it has now been adapted for use with formalin-fixed, paraffin-embedded tissue. Neoadjuvant endocrine therapy has been increasingly employed in clinical practice to improve the disease outcome [6-8], but little is known of the molecular effects of these agents. Particularly, the genetic impact of endocrine therapy directly on breast cancer remains largely unexplored. Most studies that examined the anti-estrogen treatment of ER positive breast cancer, have measured changes in clinical, pathological, proliferative or surgical outcomes [7, 25, 26] and

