This is a clinical trial with three treatment groups including tamoxifen, letrozole, and exemestane. Ten pre-menopausal patients and men will be in their own group and will receive tamoxifen. Twenty post-menopausal patients will in a separate group and will receive either letrozole or exemestane. Treatment selection will be at the discretion of the medical oncologist. Ten patients will be allocated to each treatment group, for a total of 30 patients. Full genome Mammprint will be run on the biopsy specimen and the final surgical specimen. We will then compare the gene profiling between the two results. OncoSignal pathway analysis will make use of the same biopsy specimen for evaluating the ER pathway activity scores.

The Oncosignal results will not be shared with patients(subjects), treating physicians; nor will be used for patients' management; It only will be used for research purposes.

In addition, some clinical data will be collected from the patient's medical records, operative/pathology reports, and clinical notes. This information will include information such as details of the cancer diagnosis, details of the surgery and further treatment of the disease.

Study design is illustrated in Figure 1.

Figure 1. Study Scheme

[figure not shown]

Figure 1. Study Scheme

Assays and Tests used in the study:

Mammaprint: This is a strong diagnostic tool that will be used in the study as Breast Cancer Assay and will provide invaluable information regarding the genomics of the patient and their tissue sample. We will be running the test twice to ascertain the differences between the samples due to a short term hormonal therapy course.

- OncoSignal: This is a test that measures biologically active pathway activities of 4 different pathways (ER, AR, PI3K and MAPK). In this study especially the ER-pathway activity is

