relevant since ER staining positive tumors are selected with an intend for hormonal treatment. From previous studies it is known that, although tumors can be ER positive in staining, the pathway is not always equally active (34). High ER pathway activity on the primary biopsy leads to a better response to hormonal therapy as compared to samples with a low ER activity on the primary biopsy, although all are ER staining positive. Also the change in pathway activity is higher in patients that respond to hormonal therapy as compared to patients that do not, or suboptimally respond, to hormonal treatment. The test requires 0.25mm³ FFPE tissue with a tumor percentage of at least 50%. In principle the same biopsy material can be used as collected for mammaprint but the processing of the FFPE samples is different

Study Drug Information(Dosage, Administration Frequency, Duration):

Tamoxifen: 20mg is administered daily. Patients take this drug for 2-6 weeks.

Letrozole: 2.5mg is administered daily. Patients take this drug for 2-6 weeks

Exemestane: 25mg is administered daily. Patients take this drug for 2-6 weeks.

b. Study duration and number of study visits required of research participants.

We anticipate this study to be done in 2 years. Following consent, and prescription of hormonal therapy, patients will have only one study visit prior to surgery, to take a baseline core research biopsy. The surgical sample will be used for post-treatment analysis

c. Blinding, including justification for blinding or not blinding the trial, if applicable.

d.

This is a single arm trial and so will not be blinded.

e. Justification of why participants will not receive routine care or will have current therapy stopped.

Participants will receive routine care. Normally, patients are scheduled for surgery after radiologic and other workups are completed. After surgery, they will receive hormonal therapy. In our study, hormonal therapy will commence after patients are recruited to the study and informed consent is signed, prior to surgery. Hormone therapy will continue after surgery.

f. Justification for inclusion of a placebo or non-treatment group.

There is no placebo or non-treatment group.

g. Definition of treatment failure or participant removal criteria.

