Treatment failure happens if the patient doesn't comply with the hormonal therapy treatment plan. At such cases, the patient will be removed from the study. If any patient miss more than two doses of the medication they will be removed from the study.

Because the duration of the study is short, and the medications are well tolerated, we expect very few non-compliant patients. We will add additional patients to the study if we lose any due to this clause.

- h. Description of what happens to participants receiving therapy when study ends or if a participant's participation in the study ends prematurely.

This is expected to be a rare event as patients are only followed for 2-6 weeks, until surgery, and the hormonal therapy administered in this study is well studied and carries minimal risk of long term effects or consequences. In such cases, patients will continue their standard of care plan as advised by their care providers.

5. Inclusion/Exclusion Criteria

A. Inclusion criteria:

- Treatment-naïve, histologically confirmed invasive ductal breast cancer between stages 1 to 3.
- Co-enrollment in the FLEX Registry
- ER+ PR+ confirmed hormone receptor status measured by immunohistochemistry(IHC)
- Patients should understand their condition and be able to give informed consent to participate

B. Exclusion Criteria:

- History of hormonal therapy, chemotherapy, radiation therapy, or novel therapy to treat the current breast cancer.
- Allergic reactions/hypersensitivity to tamoxifen, letrozole, or exemestane or any of their ingredients.
- Any contraindication to hormonal therapy, such as history of thromboembolic disease or uterine cancer.
- Patients without invasive disease (stage 0)
- Patients with metastatic breast cancer(stageIV)
- Patients that are HER2+ by IHC/FISH.

Drugs/ Substances/ Devices

a. The rationale for choosing the drug and dose or for choosing the device to be used.

The drugs in this study are FDA approved medications and drugs of choice for hormone therapy according to NCCN (National Comprehensive Cancer Network) guidelines. We will use the standard recommended daily doses of the drugs.

MammaPrint has 510k FDA clearance as a device and is a cost-effective vehicle for evaluating the genomic objectives of this study. The patient population considered for enrollment in this trial are candidates for receiving MammaPrint as a part of their standard of care.

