Exploratory analyses

Identify differentially expressed transcripts after short-term pre-operative, hormone treatment

Identify transcripts for which gene expression is associate with measures of response, including changes in Ki67, ER and PR expression.

We will fit empirical Bayes linear models [32] to identify genes for which expression is associated with response to treatment, controlling type I error at an FDR of <10%. Wilcoxon Rank Sum tests will be used to perform Gene set enrichment analysis on the results to identify pathways that are significantly altered after short-term treatment. [33]

Show differences in pre treatment ER pathway activity scores between patients, although all patients are ER staining positive this does not always relate to an active pathway. Show differences in ER pathway activity scores between pre and post treatment samples, indicating a measurable biological effect of the treatment.

d. Early stopping rules.

There are no early stopping rules.

6. Risks

a. Medical risks, listing all procedures, their major and minor risks and expected frequency.

Important drug adverse effects like increased risk of thromboembolism would be considered a major risk. The other non-specific side effects may be considered as minor risk. Since the drugs are administered over a short period, it is highly unlikely to develop an adverse event that requires chronic use of the drug.

The Oncosignal test has minimal risks:

It is noninvasive, does not require an invasive sampling that presents significant risk, does not introduce energy into a subject and is not used as a diagnostic procedure without confirmation of the diagnosis by another medically established diagnostic product or test

The Oncosignal results will not be shared with patients(subjects), treating physicians; nor will be used for patients' management; It only will be used for research purposes.

b. Steps taken to minimize the risks.

Known adverse effects of tamoxifen and anastrozole will be recorded using a checklist every week by the research assistant. Medical monitoring will be made by both the principle investigator and the Institutional Data and Safety Monitoring Board. Patients are informed about all common and important adverse effects and they are advised to report as soon as they notice them. They are also advised to take some preventive measures for example for the prevention of

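### The weekly adverse-effect checklist names anastrozole, which no patient receives, and omits letrozole and exemestane, planned for 20 of 30 patients

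*Combined protocol and SAP*

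**What the plan says.** The rule is in section 6 (Risks), item b: "Known adverse effects of tamoxifen and anastrozole will be recorded using a checklist every week by the research assistant".

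The rest of the protocol gives a different set of drugs:

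- Section 2 (Objectives) defines the treatment as "hormonal therapy (tamoxifen, letrozole, and exemestane, administered according to standard of care".
- Section 4a (Study design) has three groups of ten. Premenopausal patients and men receive tamoxifen; for the others, "Twenty post-menopausal patients will in a separate group and will receive either letrozole or exemestane".
- The Study Drug Information list in section 4 gives doses for tamoxifen, letrozole and exemestane only; its last entry begins "Exemestane: 25mg is administered daily".
- Section 5B (Exclusion Criteria) excludes "Allergic reactions/hypersensitivity to tamoxifen, letrozole, or exemestane or any of their ingredients".

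Outside the reference list, anastrozole appears in one other place, as a class example in section 3 (Background): "Aromatase inhibitors (e.g., anastrozole, letrozole, or exemestane) which directly inhibit the production of estrogen".

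On contact during treatment, section 4b says "patients will have only one study visit prior to surgery, to take a baseline core research biopsy".

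**The concern.** The checklist sentence is an operative instruction to the research assistant, and it is current text. Read literally, it asks for the known effects of a drug that is not in the trial and gives no instruction to record those of letrozole or exemestane.

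What is at stake is the completeness and consistency of safety recording in the two aromatase inhibitor groups. The protocol sets out no other scheduled recording of adverse effects between the start of treatment and surgery, and the single study visit in section 4b is for the baseline biopsy. A reader of the protocol cannot tell which drugs the form was built for.

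**Working it through.** This is a comparison of text plus a count.

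**Drugs named, place by place**

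| Place | Tamoxifen | Letrozole | Exemestane | Anastrozole |
|---|---|---|---|---|
| Section 2, Objectives | yes | yes | yes | no |
| Section 4a, treatment groups | yes | yes | yes | no |
| Section 4, Study Drug Information | yes | yes | yes | no |
| Section 5B, allergy exclusion | yes | yes | yes | no |
| Section 6b, weekly checklist | yes | **no** | **no** | **yes** |

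Four operative places agree with one another, and the checklist rule disagrees with all of them. Of the two drugs that the rule names, one is not given. Of the three drugs given, two are not named.

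**Patients affected**

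Inputs from section 4a: 10 patients on tamoxifen, 20 on letrozole or exemestane, 30 in total.

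- The plan's total is reproduced: 3 groups × 10 = 30, and 10 + 20 = 30.
- Patients whose drug the rule names: 10/30 = 33%.
- Patients whose drug the rule does not name: 20/30 = 67%.
- Patients planned for anastrozole: 0 of 30.
- With all three study drugs named: 30/30 = 100%.

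**Weekly entries**

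Assume one checklist per treatment week over the stated 2 to 6 weeks, with no removals or replacements.

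- At 2 weeks: 20 × 2 = 40 of 30 × 2 = 60 entries.
- At 6 weeks: 20 × 6 = 120 of 30 × 6 = 180 entries.

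The share is 67% at both ends, so these counts only rescale the patient count. They count entries for patients on a drug that the rule does not name. They do not count missed effects or defective records.

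**The case against.** The strongest reply is that this is a slip in a drug name with no demonstrated consequence.

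- **Class overlap.** Section 3 lists anastrozole together with letrozole and exemestane as aromatase inhibitors. The name may stand in for the class, and a form built around anastrozole may share items with the other two. This stands as a limit on the consequence. It does not repair the rule, because nothing in the documents says that such a form will serve for the other two drugs or that it covers them fully.
- **The rule does not exclude anyone.** It does not restrict the checklist to tamoxifen patients, and one form could be completed weekly for all 30. This also stands. The text does not say that 20 patients go unrecorded; it names the wrong drug as the source of some of the items.
- **The visit schedule proves little.** One study visit does not rule out routine clinical contact, and section 4 says that participants receive routine care. That is fair. The point rests instead on the absence of any other scheduled recording of adverse effects in the protocol.
- **Other safeguards do not depend on the drug.** Section 6b also says "Patients are informed about all common and important adverse effects and they are advised to report as soon as they notice them". It provides for monitoring by the investigator and the institutional board, for care of all adverse effects, and for patients to have the investigators' contact details. Section 6c requires unanticipated problems and deviations to be recorded and reported. These narrow the risk, but none of them is a scheduled record of known effects.
- **No objective depends on it.** Adverse effects are not a primary, secondary or exploratory outcome, and there are no early stopping rules for the checklist to feed. This is correct and is a reason to rate the point low.

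**Conclusion.** The inconsistency is real and the rule is wrong as written. It names a drug planned for none of the 30 patients and omits the drugs planned for 20 of them (67%).

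Confidence is high for the naming mismatch, which rests only on the protocol's own text and planned allocation. No claim is made that safety data would be lost. Whether any letrozole or exemestane effect is missing depends on the checklist form, which is not in the documents. The origin of the wording cannot be established either. The Ki67 analysis, the sample size and the power are unaffected. The point is minor.

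**What to change.** In section 6b, replace anastrozole with letrozole and exemestane, so that the weekly checklist covers the known adverse effects of tamoxifen, letrozole and exemestane. Then compare the checklist form with the known effects of each of the three drugs and add any missing items.

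The cost is a one-line protocol correction and a check of the form, with a form revision only if items are missing.
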